**1. Introduction and Purpose:**

It is standard practice in the United States and many parts of world to perform Gastrointestinal (GI) endoscopy with the patient under deep sedation (1). Obesity is accepted as a patient specific risk factor for hypoxic events during procedural sedation for GI endoscopic procedures. The Obese population has a higher prevalence of obstructive sleep apnea (OSA) which is characterized by repeated obstruction of the upper airway, and leads to apnea and desaturation. This prospective, randomized study was designed to compare the effectiveness of the high flow nasal cannula and the standard nasal cannula in morbidly obese (BMI > 40) patients receiving deep intravenous sedation during colonoscopies. This study will assess whether use of the high flow nasal cannula (HFNC) leads to less intraoperative desaturation events compared to the current standard of care.

**Hypothesis 1-** The HFNC group will have significantly lower incidence of desaturation episodes (SpO2 <90) than the standard nasal cannula group during procedural sedation for colonoscopies.

**Primary objective:** To compare the frequency of desaturation episodes during procedural sedation in obese patients undergoing colonoscopies.

**Hypothesis 2-** The HFNC group will require fewer interventions to treat hypoxic events than the standard nasal cannula group during procedural sedation for colonoscopies.

**Secondary objective1:** To compare the number of interventions made by the anesthesia providers required to treat desaturation events during procedural sedation in patient undergoing colonoscopies.

**Hypothesis 3-** Use of HFNC would decrease sedation-related adverse events in obese subjects with OSA.

**Secondary objective2:** To determine the frequency of desaturation episodes during procedural sedation in obese patients with undiagnosed OSA.

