All patients will receive a similar intravenous anesthetic with a propofol infusion titrated to a Richmond Agitation-Sedation Scale (RASS) score of 3-4. A lidocaine bolus of up to 100 mg can be used prior to the start of the propofol infusion for initial tolerance of the drug. Patient saturation is recorded every minute during the anesthetic on the electronic medical record and is available for review. The duration and frequency of all measurements at or below 90% will be recorded by the Electronic Medical Record (EMR). The anesthesia providers will be instructed to intervene only when the patient's saturation falls below 90%, by either manually performing a jaw thrust, placing a nasal or oral airway, bag mask ventilation, increasing the patients FiO2 or decreasing the rate/ pausing the propofol infusion or endotracheal intubation. They will be instructed to write a quick note at the time of intervention in the EMR describing their maneuver. Duration of the study will be the length of the procedure through discharge from the Postoperative Anesthesia Care Unit (PACU).

Our hypothesis is that the patients in the high flow nasal cannula group will experience a marked reduction in intraoperative desaturation events as compared to the Salter cannula group.

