#### **Outcome Measures:**

- Lowest recorded saturation
- The frequency of desaturation episodes (SpO2 <90%)
- Duration of desaturation episodes (SpO2 <90%)
- Number of apnea episodes
- Dose of propofol or other combination for sedation during colonoscopy
- Anesthesiologist intervention (intubation, airway repositioning, Chin lift)
- Type of airway used (oral airway, nasal airway, bag mask ventilation, suctioning)
- Premature termination of procedure
- Unplanned hospital admission

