#### **4. Study Procedures:**

- OSA screening with the SB questionnaire: SB is made up of 8 yes or no questions (14). The anesthesiologist or certified registered nurse anesthetist will be blinded to the results of the SB.

High risk of obstructive sleep apnea if yes to  $\geq 5$  questions; low risk of obstructive sleep apnea: yes to  $\leq 4$  questions.

- Randomization to the high flow nasal cannula group or the Salter cannula group. Subjects will be randomized in a 1:1 ratio according to a computer generated randomization list provided by the study statistician.
- All standard monitoring (BP, EKG, pulse oximeter) placed on all patients in the procedure room. Cannulas placed on the patients 5 minutes prior to the start of the anesthetic and set to rate of 4/min for standard nasal cannula and 36% FiO2 up to 60 L/min for the HFNC group.
- Anesthesia achieved with a propofol infusion titrated to a RAS score of 3-4.
- All desaturation points at or below 90% recorded via intraoperative electronic charting (Epic).
- Frequency and method of intervention aimed at increasing the patient's saturation by the provider will be recorded on the EMR at the time of intervention with a quick note.

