## 8. Sources of Research Material:

- Subjects undergoing colonoscopy
- Electronic Medical Record
- Anesthesia Reports
- PHI including name, medical record number, contact information including demographic information including age, gender, race, birth date, weight, height, BMI and medical and surgical history, medication list, ASA classification.
- **Procedural sedation-related variables:** type of sedation agent used for procedural sedation, propofol dose, propofol infusion time, opioid use, any other combination agent for the procedural sedation during colonoscopy, Procedure time, premature termination of procedure.
- **Respiratory event-related variables;** Anesthesiologist intervention (intubation, airway repositioning, Chin lift); Type of airway used (oral airway, nasal airway, bag mask ventilation, suctioning), Laryngospasm or any other airway obstruction; pulse oximetry reading, the number and duration of apnea/hypoxia episodes.
- **Hemodynamic variables** such as baseline blood pressure
- **Postoperative Recovery:** Aldrete score in recovery, the time spend in PACU
- Unplanned hospital admission

- Stop Bang questionnaire for OSA screening

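### The below-90% intervention rule in Section 3 states no exception for an airway emergency at a saturation of 90% or more

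*Combined protocol and SAP*

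**What the plan says.** The rule stands in Section 3 (Concise Summary of Project): "The anesthesia providers will be instructed to intervene only when the patient's saturation falls below 90" percent. The maneuvers it then names are jaw thrust, a nasal or oral airway, bag-mask ventilation, more inspired oxygen, a slower or paused propofol infusion, and intubation. The same section calls for a "propofol infusion titrated to a Richmond Agitation-Sedation Scale (RASS) score of 3-4" and sets out how interventions are charted: "They will be instructed to write a quick note at the time of intervention in the EMR describing their maneuver".

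The plan foresees airway events without tying them to a saturation. The Outcome Measures list includes "Number of apnea episodes", and Section 8 collects "Laryngospasm or any other airway obstruction; pulse oximetry reading, the number and duration of apnea/hypoxia episodes".

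Other sections bear on what the rule was meant to cover. In Section 1, Hypothesis 2 reads "The HFNC group will require fewer interventions to treat hypoxic events than the standard nasal cannula group during procedural sedation for colonoscopies", and the matching objective is "To compare the number of interventions made by the anesthesia providers required to treat desaturation events". Section 4 says "Frequency and method of intervention aimed at increasing the patient's saturation by the provider will be recorded on the EMR" and does not repeat the restriction. Section 14 compares mean numbers of interventions for hypoxic events. Section 10 states that anesthetic care in both arms matches usual practice. Section 11 commits the investigators to patient safety and to all standards of care, and mentions provider interventions in connection with marked desaturation.

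**The concern.** A fixed trigger is a sensible way to standardize rescue when the endpoint is a saturation below 90%. The difficulty is the word *only*, combined with a list that covers most of what a provider can do for an airway. Section 2 itself attributes desaturation in sleep apnea to airway narrowing and obstruction, so the airway problem may come before the low reading. A provider who follows the sentence exactly would wait for the reading to fall before treating laryngospasm, complete obstruction or sustained apnea.

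Two things are at stake. The first is possible delay of rescue in deeply sedated, morbidly obese patients. The second is consistency: two careful providers could read the same protocol differently, and the chart note need only describe the maneuver, not why it was done. Early action can prevent a reading below 90%, which is the primary event, and it adds to the intervention count compared in Section 14.

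**Working it through.** The point turns on the text, so most of the check sets sections side by side. The plan's one relevant calculation comes first, to see whether the point depends on it.

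**1. Sample size (Section 14).** Inputs: 51% in controls, a 25-point difference (so 26% with HFNC), 80% power, alpha 0.05 taken as two-sided, and 1:1 allocation (Section 4). The pooled formula without continuity correction uses a mean proportion of (0.51 + 0.26)/2 = 0.385:

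n = [1.96 × √(2 × 0.385 × 0.615) + 0.842 × √(0.51 × 0.49 + 0.26 × 0.74)]² / 0.25² = 58.3, rounded up to 59 per group.

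This matches the plan; power at 59 per group is 80.5%. Enrollment is 118 × 1.10 = 129.8, or 130, as stated. No input describes a rescue policy, so neither the concern nor the fix changes these figures.

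**2. Is there an exception anywhere?**

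| Place | What it contributes | Does it lift the restriction? |
|---|---|---|
| Section 3 | The rule and its list of maneuvers | No exception stated |
| Section 3, sedation target | Propofol must be titrated, so its rate may need lowering at any saturation | Shows the rule cannot be wholly literal; silent on airway emergencies |
| Section 1 and Section 14 | Interventions counted are those for hypoxia or desaturation | Suggests purpose; gives no permission |
| Section 4 | Interventions aimed at raising saturation | Omits the restriction; does not cancel it |
| Section 10 | Care as usual in both arms | General; claims no precedence |
| Section 11 | Safety and standards of care; interventions mentioned with desaturation | General; claims no precedence |

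No section states an exception, and none says which text governs if they conflict.

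**3. Are the uncovered situations foreseen?** Yes. Apnea is a listed outcome, and laryngospasm and airway obstruction are collected variables, with no saturation condition attached.

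**4. Can the frequency be estimated?** That would need the rate of airway emergencies at a saturation of 90% or more, and the share of providers who would wait. The documents give neither, so no figure or range is offered.

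**5. Would the record show what happened?** In part. Section 3 has saturation charted every minute, so the value near an intervention could be recovered. The reason for acting is not required, and nothing links a recorded airway event to a particular maneuver.

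**The case against.** The strongest reply is that the narrow reading is the intended one. The sentence follows directly on text about recording saturation, the objectives and the analysis concern treatment of desaturation, and titration to a sedation target already breaks the literal reading. The restriction sits in a summary section and is missing from Study Procedures. The Outcome Measures list and Section 8 name chin lift, repositioning and suctioning, which the Section 3 list omits, so that list may not describe all airway care. Section 11 opens with a duty to keep patients safe throughout, and its mention of desaturation does not say that interventions are confined to it.

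Much of this stands. It makes the narrow reading plausible, and experienced providers may well act early whatever the sentence says. It does not remove the ambiguity: the only explicit instruction on when to intervene says *only* and has no stated exception.

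A second objection also stands. An exception for any obstruction or apnea, neither of which the plan defines, could swallow the rule. Section 4 blinds providers to the STOP-BANG result but not to the device, and the high-flow rate is titrated to tolerance, so they can be expected to know the arm. A loose exception would let them avert primary events at their discretion. The exception therefore has to be confined to emergencies and each use recorded.

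**Conclusion.** The point holds as a gap in the wording with a patient-safety consequence: an explicit restriction, general safeguards that do not say they override it, and no exception for an airway emergency. It assumes only that some provider might take the sentence at its word. The instruction applies to all 130 planned patients; the number who would be affected is unknown, and on the narrow reading it is zero.

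A reader might infer three stronger things, none of which the documents support.

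- *That the trial plans to withhold rescue.* Sections 10 and 11 point the other way, and several sections fit a narrower purpose.
- *That about 45 patients are at risk.* At the planning rates, 59 × 0.51 = 30.1 and 59 × 0.26 = 15.3, about 45 of 118. That is only the expected number of primary events. It is not a ceiling: the 51% comes from a 79-patient study under conscious sedation (Section 2) whose rescue policy is not given, literal delay could push the rate higher, and the sum covers 118 patients, not 130.
- *That the primary result is biased in a known direction.* Both the size and the direction of any effect are unknown.

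Label: cheap improvement (patient safety).

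**What to change.** Keep the below-90% trigger as the standard rule for both arms, and add to Section 3:

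> *Providers may intervene at any SpO2 for laryngospasm, complete airway obstruction, sustained apnea or other immediate threat to the patient, and may adjust propofol to the RASS target.*

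Have the note that providers already write give the saturation and the reason for the intervention. Report interventions made at a saturation of 90% or more by arm, descriptively. The primary outcome, its test and the sample size stay as they are.

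The cost is one sentence, two items in an existing note and one descriptive line in the report. There is a real downside: a few early rescues by providers who know the arm may avert a primary event. The by-arm report would show this but would not correct for it.

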#### **Outcome Measures:**

- Lowest recorded saturation
- The frequency of desaturation episodes (SpO2 <90%)
- Duration of desaturation episodes (SpO2 <90%)
- Number of apnea episodes
- Dose of propofol or other combination for sedation during colonoscopy
- Anesthesiologist intervention (intubation, airway repositioning, Chin lift)
- Type of airway used (oral airway, nasal airway, bag mask ventilation, suctioning)
- Premature termination of procedure
- Unplanned hospital admission

#### **4. Study Procedures:**

- OSA screening with the SB questionnaire: SB is made up of 8 yes or no questions (14). The anesthesiologist or certified registered nurse anesthetist will be blinded to the results of the SB.

High risk of obstructive sleep apnea if yes to  $\geq 5$  questions; low risk of obstructive sleep apnea: yes to  $\leq 4$  questions.

- Randomization to the high flow nasal cannula group or the Salter cannula group. Subjects will be randomized in a 1:1 ratio according to a computer generated randomization list provided by the study statistician.
- All standard monitoring (BP, EKG, pulse oximeter) placed on all patients in the procedure room. Cannulas placed on the patients 5 minutes prior to the start of the anesthetic and set to rate of 4/min for standard nasal cannula and 36% FiO2 up to 60 L/min for the HFNC group.
- Anesthesia achieved with a propofol infusion titrated to a RAS score of 3-4.
- All desaturation points at or below 90% recorded via intraoperative electronic charting (Epic).
- Frequency and method of intervention aimed at increasing the patient's saturation by the provider will be recorded on the EMR at the time of intervention with a quick note.

## 5. Sub-Study Procedures:

N/A

## 6. Criteria for Inclusion of Subjects:

- Age between 18-80
- Subjects undergoing colonoscopies
- Morbidly obese BMI  $\geq 40$

## 7. Criteria for Exclusion of Subjects:

- Subjects deemed hemodynamically unstable by the anesthesia team
- Subjects who are an aspiration risk and will require endotracheal intubation.
- Pregnancy
- Subjects with an allergy to propofol
- Patients who are unable to tolerate the high flow nasal cannula secondary to discomfort
- Subjects unwilling to sign consent
- Chronic obstructive pulmonary disease
- Patients that received medications other than lidocaine and propofol

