**3. Concise Summary of Project:** The study population for this randomized prospective clinical trial will consist of male and female subjects, between the ages of 18-80, with a BMI over 40 undergoing colonoscopies. Consent will be obtained by research coordinator or anesthesia providers involved in

the study. OSA screening questionnaire (Stop Bang) will be completed during review of the patient's history and physical exam and subjects will be stratified based on STOPBANG score of  $\geq 5$  versus  $\leq 4$ . Subjects will then be randomized in a stratified fashion to either the HFNC (Comfort Flo System) group or the Salter cannula group. Then subjects will be brought into the procedure room and placed on all standard ASA monitors (BP cuff, EKG, pulse oximetry). In the HFNC group, the nasal cannula will be placed on the patient at a setting of FiO2 36% and up to 60L/min depending on patient tolerance. 60 L/min is the max flow rate and will be used as tolerated for maximum benefit. The HFNC setting will start at 40 L/min and will be titrated up to the max flow rate of 60 L/min depending on subjects' tolerance.

**Research intervention:** The Comfort Flo system (Teleflex Medical, Research Triangle Park, NC, USA) will be used for high flow nasal cannula during colonoscopy. The Comfort Flo System has an air-O2 blender setting and a FiO2 analyzer to confirm FiO2 delivered to the patient. This FiO2 has been shown to be equal to the FiO2 measured using the Salter cannula at 4L/min (13).

Control group: A Salter nasal cannula will be used at 4L/ minute during the colonoscopy.

The cannulas will be placed on the patients 5 minutes prior to the start of the anesthetic.

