### **9. Recruitment Methods and Consenting Process:**

All patient recruitment will take place in the GI endoscopy suite. Subject will be identified by reviewing daily endoscopy schedule. A designated team of anesthesiologists and nurse anesthetists involved in the study will be responsible for screening, consenting and enrolling potential subjects. The patient's chart will be reviewed to determine eligibility with the use of a HIPAA waiver form. Information about the study will be given in a pressure-free, confidential private area in a face-to-face meeting and the voluntary nature of the research will be emphasized to the subjects.

The purpose of the study and risks and potential complications of the study will be explained. Adequate time will be given to read consent form to consider whether or not participate in the study. All questions will be answered before the patient is asked to sign the consent form. If the patient agrees to participate, then he or she will sign the consent form and HIPAA Authorization Form prior to any study procedures.

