#### **Risk for HFNC:**

There may be minimal risk for mucosal injury with HFNC. This risk is not higher than standard nasal cannula because HFNC systems deliver heated, humidified gas.

HFNC may produce distending pressure in the lung, similar to CPAP pressures. There may be potentially unpredictable pressures generated by HFNC which may be significant in pediatric but not adult obese population. Mild distending pressure may provide better patent airway in obese subjects. Flow rate of HFNC will be adjusted for maximum benefit to the subject (40-60 L/minutes).

**Psychological Stress:** Some of the questions related to the study may make the subject feel uncomfortable. Subjects may refuse to answer any of the questions, or take a break or stop participation in the study at any time.

**Loss of Confidentiality:** Any time information is collected; there is a potential risk of loss of confidentiality. Every effort will be made to keep your information confidential.

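### HFNC intolerance is listed as an exclusion but, unless already known, can be met only after randomisation and only in the HFNC arm, and no analysis-set rule keeps those patients in

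*Combined protocol and SAP*

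**What the plan says.** Section 7 lists among the exclusions: "Patients who are unable to tolerate the high flow nasal cannula secondary to discomfort". It does not say when this is to be judged.

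Section 3 gives the order of events. After consent and the STOP-BANG questionnaire, "Subjects will then be randomized in a stratified fashion to either the HFNC (Comfort Flo System) group or the Salter cannula group". Patients then enter the procedure room and are monitored, and "The cannulas will be placed on the patients 5 minutes prior to the start of the anesthetic". Section 4 lists "Randomization to the high flow nasal cannula group or the Salter cannula group" ahead of monitoring and cannula placement. The control arm receives a Salter cannula at 4 L/min and never HFNC. In the HFNC arm the flow starts at 40 L/min and goes "up to 60L/min depending on patient tolerance".

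Section 9 says that the patient's "chart will be reviewed to determine eligibility". No tolerance test before randomisation is described.

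Section 14 compares desaturation proportions between the two groups with a Z test or Fisher's exact test. It names no intention-to-treat, modified or per-protocol set, and has no rule for a randomised patient who later meets an exclusion. It allows a 10% loss without saying what is lost, in a study that, by Section 3, ends at discharge from the PACU.

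A second Section 7 item excludes patients given drugs beyond lidocaine and propofol, also without a time window. The outcome list in Section 3 and the data list in Section 8 collect other sedation agents, and Section 8 also collects opioid use.

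**The concern.** An eligibility criterion is harmless when it is settled before allocation. This one depends on a device that only one arm receives, after allocation. A Salter patient who would have been equally intolerant is never tested and stays in. Used as a reason to remove patients, the criterion acts on one arm alone, and the decision would be made with the assignment known.

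The primary test would then no longer compare the groups as randomised. Discomfort in the minutes before sedation is not itself caused by desaturation, so removal biases the comparison only if intolerance is related to desaturation risk. Nothing in the documents shows whether it is.

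**Working it through.** **1. The plan's own figure.** Inputs from Section 14: control risk 0.51, a 25-point difference (so HFNC 0.26), 80% power, type 1 error 0.05, taken as two-sided. The pooled normal formula is

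n = [1.96·√(2·p̄(1−p̄)) + 0.842·√(p1(1−p1) + p2(1−p2))]² / (p1−p2)², with p̄ = (0.51 + 0.26)/2 = 0.385.

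It gives 58.3, so 59 per group, as stated. Enrolment is 118 × 1.10 = 129.8, so 130, or 65 per arm.

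**2. Can the criterion be met symmetrically?**
- Known before randomisation: yes, in either arm, through chart review or the patient's own report.
- Not known before randomisation: only when HFNC is applied, which is after allocation and in one arm.
- Partial intolerance: absorbed by adjusting flow to tolerance. What remains is the patient who cannot tolerate the device at all, for whom no analysis rule is given.

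**3. Effect of removing these patients when HFNC does nothing.** Assumptions not in the documents: the share f of the HFNC arm excluded, and their event risk r. I take f = 5%, 10% and 20%, and r within 20 points either side of 51%. The 10% and 20% shares are tied to the loss allowance: 10% of 130 is 13 patients, which is 10% of the HFNC arm if spread evenly and 20% (13/65) if all fall there.

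Risk in the remaining HFNC patients = (0.51 − f·r)/(1 − f). Example: f = 0.10, r = 0.71 gives (0.51 − 0.071)/0.90 = 0.488, an apparent reduction of 2.2 points.

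The test is the pooled two-sided 0.05 Z test, evaluated by exact binomial enumeration with all 65 Salter patients. The interim look and any Bonferroni correction are ignored.

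| HFNC excluded | Analysed (Salter v HFNC) | Largest shift | False result favouring HFNC: r = 31% | r = 51% | r = 71% | Two-sided error at r = 71% |
|---|---|---|---|---|---|---|
| 5% | 65 v 62 | 1.1 points | 1.9% | 2.6% | 3.3% | 5.2% |
| 10% | 65 v 58 | 2.2 points | 1.4% | 2.6% | 4.4% | 5.8% |
| 20% | 65 v 52 | 5.0 points | 0.6% | 2.6% | 7.9% | 8.5% |

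With nobody excluded (65 v 65) the figure is 2.2%. The 2.6% at r = 51% differs from it only because the test is discrete and the arms are unequal. That column carries no bias.

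**4. What keeping these patients costs.** Assume 10% of the HFNC arm is intolerant and has the Salter risk. The HFNC rate becomes 0.90 × 0.26 + 0.10 × 0.51 = 0.285. Exact power against 0.51 falls from 0.80 to 0.71 at 59 per arm, and from 0.85 to 0.76 at 65 per arm. At 5% intolerant the rate is 0.95 × 0.26 + 0.05 × 0.51 = 0.2725, with power 0.76 and 0.81.

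**The case against.** The strongest reply is that Section 7 is a screening list, that Section 9 has the chart reviewed for eligibility, and that flow is set to tolerance, so few patients are left. Nowhere do the documents say that a randomised patient is removed from the analysis. This much stands: a reader might infer that the plan drops intolerant HFNC patients, and the text does not support that. It lists the criterion, gives it no timing, and has no rule that would prevent such use.

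A reader might also infer that the 10% allowance is meant for intolerance, or that the result will be tilted towards HFNC. Neither follows. The allowance has no stated cause. If intolerant patients have lower risk than average, the tilt runs against HFNC.

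The one-sided figures can also look more alarming than they are. Against a nominal 5%, two-sided error moves to only 5.2% or 5.8% at the extreme assumed risk unless a fifth of the arm is removed. This limits the weight of the point but does not close the gap.

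On the medication item, a reader might see a flat contradiction with Sections 3 and 8. Recording an agent is also how a criterion on that agent is checked, so collecting the data does not by itself contradict the exclusion. What remains is an unclear time window, and that item is not specific to one arm.

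**Conclusion.** The point holds as a conditional one and should be fixed. As written, the intolerance exclusion can remove randomised patients from the HFNC arm alone, and Section 14 does not stop it. That conclusion rests on the order of procedures and the absence of an analysis set, both plain in the text, and confidence in it is high.

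Confidence does not extend to a material bias. Under the assumptions tabulated, the distortion is small at 5% or 10% excluded. It becomes appreciable only if about 20% of the HFNC arm is removed and their risk is clearly different from average. The actual size and direction cannot be worked out from the documents.

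**What to change.** - **Section 7:** limit the HFNC-intolerance criterion to intolerance known before randomisation.
- **Section 14:** state that the primary analysis includes all randomised patients with outcome data, in their assigned arm. This covers HFNC patients who could not tolerate the device but were sedated, using their observed SpO2. The data will exist: "Patient saturation is recorded every minute during the anesthetic on the electronic medical record". No values need to be imputed for patients whose saturation was recorded.
- **Reporting:** list by arm, with reasons, any randomised patient who had no sedation and so has no outcome. Report how many HFNC patients could not tolerate the device.
- **Sensitivity:** a tolerant-only set may be kept, labelled as such.
- **Loss:** say what the 10% covers.
- **Medication item, separately:** Section 7 must be reconciled with the outcome list in Section 3 and the data list in Section 8, including the time window. The item should not be used to drop randomised patients from the primary analysis.

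The cost is a few sentences and some dilution of the effect. In the 10% case above, power falls below the planned 80% even with all 65 per arm analysed; in the 5% case it stays above 80% at 65 per arm. The sponsor should see that trade-off when adopting the rule.
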